5.0 Inclusion and Exclusion Criteria/ Study Population

- **Inclusion**
 - Undergoing elective spine surgery involving 4 levels or less of the thoracic, lumbar, or sacral spine.
 - 18 years of age and older.
- **Exclusion**
 - Less than 40kg in weight.
 - Unable to provide written, informed consent.
 - History of an adverse or anaphylactoid reaction to acetylcysteine.
 - Active asthma, wheezing, or using inhaled bronchodilators.
 - Pregnant Women
 - Known blood clotting deficiency
 - Insulin dependent diabetes

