10.0 Study Design / Methods

Design: This prospective, double blinded clinical trial will randomize patient to receive placebo (0.45% NaCl or 0.9% NaCl) or NAC (50, 100, or 150 mg/kg). The randomization will be created by a statistician and shared with Investigational Drug Services (IDS) pharmacy prior to patient enrollment.

IDS pharmacy has planned to set up the study to be dispensed from the main OR pharmacy. IDS will prepare numbered kits containing NAC or placebo based on the randomization scheme. The kits will be stored in the OR pharmacy and dispensed based on the assigned subject number. This will allow enrollment any time of day that the OR pharmacy is open.

Groups: Patients will be randomized to receive NAC: 0 mg/kg (placebo; 0.45% NaCl or 0.9% NaCl), 50 mg/kg, 100 mg/kg, and 150 mg/kg (Max dose 15,000 mg). The maximum dose considered will be 150 mg/kg as this has been studied for safety in numerous patient populations including those with severe comorbidities. As NAC may be reconstituted in D5W or 0.45% NaCl, we will reconstitute all NAC doses in 250ml 0.45% NaCl or D5W. We will use 250ml 0.45% NaCl or 0.9% NaCl without NAC as our placebo.

Enrollment:

Following confirmation of informed written consent, patients will be assigned an enrollment number and randomized using the randomization, created by a statistician, to one of four IV NAC groups: 0 mg/kg (placebo; 0.45% NaCl or 0.9% NaCl), 50 mg/kg, 100 mg/kg, or 150 mg/kg. Patients will proceed to the operating room where they will receive general anesthesia for their planned, elective surgical procedure. Intraoperatively, the designated IV NAC or placebo infusion will be initiated and completed by a clinical care team member. Patients will only receive NAC once as a single dose that will run over 60

minutes. Patients will be monitored in the operating room while receiving NAC and in the PACU postoperatively consistent with our standard perioperative care at MUSC.

The recorded anesthesia stop will mark time zero. The primary end point will be 12-hour postoperative opioid consumption.

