Patient and procedural characteristic will be recorded throughout the perioperative period. Demographic data (age, gender, race, weight, height, body mass index) and preoperative opioid consumption will be collected after completion of informed consent (yes or no; and consumption quantified if applicable). Surgical data (operative procedure and surgical duration) will be collected after surgery. Time of hospital discharge will be collected after the patient is discharged from the hospital.

Other exploratory outcomes will be collected as long as the patient is still in the hospital and able to self-report up to 48 hours post-operatively. Data will be collected from subject self-reporting their VAS score and using the electronic medical record. These data include intraoperative opioid consumption, postoperative anesthesia care unit (PACU) opioid consumption cumulative, non-opioid analgesic administration, postoperative opioid consumption up to 48 hours or discharge. VAS pain scores will be recorded pre-operatively, post operatively and at 24 hours unless discharged prior to 24 hours post operatively.

In order to identify the optimal IV NAC dose for perioperative opioid reduction and estimate the difference in opioid consumption between placebo and the selected optimal dose, the study will progress in two phases.

- In the first phase (20 subjects), we will attempt to identify the optimal dose. The optimal dose is defined as the dose or doses of NAC for which a $\geq 20\%$ reduction in opioid consumption relative to placebo is expected based on the dose response curve. If 20% reduction is not achieved, the optimal dose will be the maximum dose (150 mg/kg) administered during the study.
- In the second phase, after finding the optimal dose, 15 additional patients will be randomized to placebo and 15 to the optimal dose to estimate the difference in opioid consumption between patients on placebo vs. the optimal dose (30 subjects). A sample size of 20 subjects per group (5 from phase 1 and 15 from phase 2) allows us to estimate a 95% confidence interval for the mean difference in opioid consumption with a width of ± 0.64 standard deviations from the mean.
- If we are unable to create a dose response curve following the enrollment of the first 20 subject, an additional 20 subjects (5 per group) will be enrolled to create the dose response curve prior to starting the second phase.

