A pilot trial to determine the effective dose of N-acetylcysteine for opioid reduction in patients undergoing spine surgery.

NCT04562597

Statistical Analysis Plan Date: June 1, 2020

A pilot trial to determine the effective dose of N-acetylcysteine for opioid reduction in patients undergoing spine surgery.

Statistical Analysis Plan

An *a priori* sample size calculation was conducted to determine the precision of the estimated mean difference in opioid consumption at 12-hours between treatment groups in phase 2 for a fixed sample size. A sample size of 20 subjects per group was needed to estimate a 95% confidence interval for the mean difference in opioid consumption with a width of + 0.64 standard deviations from the mean.

The primary outcome of interest in phase 2 was opioid consumption at 12-hours postoperative. Additional opioid outcomes included opioid consumption over time (every 6 hours postoperatively up to 48 hours) and difference in opioid consumption between groups. Mean differences between treatment groups in opioid consumption at different postoperative times, including the primary outcome of 12 hours postoperative, were estimated from a linear mixed model including fixed effects for group, postoperative time, and their interaction and a random patient effect to account for correlation between measures collected on patients over time.

Descriptive statistics were calculated for patient and procedural characteristics across all treatment groups in phases 1 and 2. Additional phase 2 outcomes included time to first PACU opioid rescue dose, PACU VAS pain score, postoperative NRS pain scores, PACU duration, and time to hospital discharge.

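### The primary 12-hour model leaves out preoperative opioid consumption, which is already collected; pre-specifying it would correct chance imbalance and narrow the expected interval if its correlation with the outcome exceeds about 0.17

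*SAP*

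**What the plan says.** The SAP's primary model for the 12-hour difference is a linear mixed model "including fixed effects for group, postoperative time, and their interaction and a random patient effect". It names no baseline covariate and no adjusted or sensitivity model. Patient and procedural characteristics are to be described only.

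Protocol section 10.0 states that "preoperative opioid consumption will be collected after completion of informed consent (yes or no; and consumption quantified if applicable". Consent precedes randomisation and the infusion is given during surgery, so treatment cannot affect this variable.

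Section 5.0 admits patients "Undergoing elective spine surgery involving 4 levels or less of the thoracic, lumbar, or sacral spine" and does not list opioid use among the exclusions. On allocation, section 10.0 says "The randomization will be created by a statistician and shared with Investigational Drug Services (IDS) pharmacy prior to patient enrollment"; no stratification factor is mentioned there or elsewhere.

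The sample size rests on precision alone. The SAP states "A sample size of 20 subjects per group was needed" for a "95% confidence interval for the mean difference in opioid consumption", and gives its size as "with a width of + 0.64 standard deviations from the mean" (printed with a plus-or-minus sign in Protocol sections 6.0 and 10.0).

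**The concern.** Preoperative opioid consumption measures the same kind of quantity as the primary outcome, in a population that will mix users and non-users. As the documents stand, neither the described design nor the analysis makes use of it.

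The trial is judged by the width of one interval. If preoperative use predicts 12-hour use, part of that width is avoidable. With 20 patients per arm, a chance excess of users in one arm would also move the estimated difference, and nothing in the model would correct it. Adding a covariate only after an imbalance has been seen would be data-driven, so the decision has to be made in advance.

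**Working it through.** **Inputs.** There are 20 patients per arm (SAP). Both enrolment paths in Protocol section 6.0 arrive there: 5 + 15, or 10 + 10. The interval is two-sided 95% (SAP), and the outcome SD is set to 1. The within-arm correlation r between preoperative and 12-hour consumption is not in the documents; 0 to 0.6 is assumed.

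**1. The plan's own figure.** Unadjusted half-width = t(0.975, 38) × √(2/20) = 2.0244 × 0.3162 = 0.640 SD. This matches the stated 0.64. It is a single-time-point, unadjusted figure.

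**2. With one covariate.** Half-width = t(0.975, 37) × √[(2/20) × (1 − r²) × (1 + 1/36)]. The factor 1 + 1/36 is the cost of estimating the slope with 40 patients, and t(0.975, 37) = 2.0262.

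- At r = 0: 2.0262 × √(0.1 × 1.0278) = 0.650.
- At r = 0.5: 2.0262 × √(0.1 × 0.75 × 1.0278) = 0.563.

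**3. Break-even.** Setting step 2 equal to step 1 gives 1 − r² = (36/37) × (2.0244/2.0262)² = 0.971, so r = 0.170.

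**4. Chance imbalance.** The difference in covariate means between arms has SD √(2/20) = 0.316 covariate SDs. It shifts the unadjusted estimate by r times its size, so the shift has SD 0.316r. The last column of the table is 2 × [1 − Φ(0.2/(0.316r))].

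| r | Adjusted half-width (SD) | Change from 0.640 | Equivalent n per arm, 20 × (0.640/half-width)² | Adjusted interval narrower (simulated) | Imbalance shift > 0.2 SD |
|---|---|---|---|---|---|
| 0 | 0.650 | +1.5% | 19.4 | 20% | 0% |
| 0.1 | 0.646 | +1.0% | 19.6 | 28% | <0.1% |
| 0.2 | 0.637 | −0.6% | 20.2 | 47% | 0.2% |
| 0.3 | 0.620 | −3.2% | 21.3 | 69% | 3.5% |
| 0.4 | 0.595 | −7.0% | 23.1 | 87% | 11% |
| 0.5 | 0.563 | −12.1% | 25.9 | 96% | 21% |
| 0.6 | 0.520 | −18.8% | 30.4 | 99% | 29% |

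An imbalance beyond 0.5 covariate SD in either direction has probability 11.4%. One of exactly 0.5 SD shifts the estimate by 0.15 SD at r = 0.3 and 0.25 SD at r = 0.5.

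**5. Simulation.** In 40,000 trials with a normal covariate, root-mean-square adjusted half-widths at r = 0, 0.3, 0.4, 0.5 and 0.6 were 0.650, 0.619, 0.595, 0.563 and 0.520. Coverage was 0.949 to 0.953. With a skewed covariate that was zero in 60% of patients (15,000 trials), adjusted and unadjusted widths were equal at r = 0.17. At r = 0.5 the root-mean-square half-width fell from 0.641 to 0.562.

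**6. Repeated measures.** The simulation used eight times (6-hourly to 48 hours), an assumed intraclass correlation of 0.6 and 3,000 trials. With a covariate-by-time term, the SD of the 12-hour estimate relative to unadjusted was 0.97 to 0.98 at r = 0.3 and 0.88 at r = 0.5. With a main effect only, and a covariate effect that fades after 12 hours, it was 0.98 and 0.89.

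**The case against.** The strongest reply is that the documents give no value of r, so no particular gain can be claimed. At r = 0.3 the benefit is little more than one patient per arm. This stands as a limit on the size of the gain. It does not remove the asymmetry between an expected loss of at most 1.5% and a gain of 12% at r = 0.5.

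The threshold of 0.17 concerns expected width in a single-time-point analysis. At that value the realised interval was narrower in only about 40% of simulated trials, and no break-even was derived for the mixed model itself. Both qualifications are right. The plan's own 0.64 is, however, also a single-time-point figure, and the repeated-measures check points the same way.

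Under randomisation the unadjusted interval already allows for chance imbalance. That is correct: the shift probabilities and the avoidable width are two views of one variance component and should not be added together. Adjustment removes only the measured, linear part of an imbalance. The 0.2 SD cut-off is illustrative.

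Silence on stratification does not prove there was none; what can be said is that none is described. The interaction with time added little over a main effect in the setting checked, so it is the less essential part of the remedy. Finally, this is a pilot whose stated precision is met without adjustment. The omission is therefore a missed improvement, not an error.

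**Conclusion.** The concern holds as a recommended improvement. The planned analysis is valid and its stated precision is correct. It leaves unused a pre-treatment measure that is already collected, and so gives up possible precision on the one quantity that justifies the sample size.

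How much is given up depends on r, which is an assumption here. Across r = 0 to 0.6 the expected half-width runs from 0.650 to 0.520 SD against 0.640 unadjusted, with break-even at 0.17. The gain is small at r = 0.3 and material from about 0.4. These figures assume a roughly linear relation, 20 patients per arm and a single-time-point approximation at 12 hours.

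**What to change.** Add preoperative opioid consumption and its interaction with postoperative time as pre-specified fixed effects in the primary model. Code non-users as zero and fix the scale in advance, for example log(1 + daily morphine equivalents). Define the unit, the conversion and the look-back window in the SAP, since the protocol says only that the amount is quantified. Report the unadjusted 12-hour difference as supportive.

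With complete data and categorical time, the interaction makes the 12-hour estimate equal to the single-time-point covariate-adjusted one. If a leaner model is preferred, a main effect alone gave nearly the same gain in the check above; whichever is chosen should be stated beforehand.

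The cost is a short SAP paragraph and no new data item, although it should be confirmed that the recorded amounts support the chosen unit. The model gains up to eight fixed-effect terms if the eight times are categorical, or two if time is linear. If the covariate turns out not to be predictive, the expected 12-hour interval is about 1.5% wider (single-time-point approximation).

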4.0 Study Endpoints

- The primary outcome will be 12-hour postoperative opioid consumption.
- The secondary outcome will be 6-hour postoperative opioid pain score.
- Other exploratory outcomes will include intraoperative opioid consumption, postoperative anesthesia care unit (PACU) opioid consumption cumulative, non-opioid analgesic administration, postoperative opioid consumption at additional time points, and VAS pain scores at additional time points.
- Other collected data will include patient demographic data, surgical data (procedure, operative duration), preoperative opioid consumption, time to hospital discharge.

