Descriptive statistics by treatment group were calculated to allow for comparisons between groups. Average NRS pain score over postoperative time within and between groups was estimated from a linear mixed model including fixed effects for treatment group, postoperative time at pain score measurement, and their interaction as well as a random subject effect to account for correlation between pain scores collected on the same patient over time. Confidence intervals for the median time to first opioid rescue dose was estimated using the Brookmeyer-Crowley approach using the log-log complement transformation.²³ Confidence intervals for the median PACU and hospital length of stay confidence limits are calculated using the distribution free approach described by Hahn and Meeker.²⁴ All analyses were conducted in SAS v. 9.4 (SAS Institute, Cary NC, USA).

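### Pre-operative VAS pain is planned for collection but not used in the SAP's pain analyses, which gives up some precision in exploratory comparisons

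*SAP*

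**What the plan says.** **Baseline.** Protocol Section 10.0 sets the pain schedule: "VAS pain scores will be recorded pre-operatively, post operatively and at 24 hours unless discharged prior to 24 hours post operatively". The one exception it states, early discharge, concerns the 24-hour score.

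**Outcomes.** The SAP lists the additional phase 2 outcomes as "time to first PACU opioid rescue dose, PACU VAS pain score, postoperative NRS pain scores, PACU duration, and time to hospital discharge".

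**Analysis.** NRS pain over time is analysed with a linear mixed model whose terms are "fixed effects for treatment group, postoperative time at pain score measurement, and their interaction as well as a random subject effect". PACU VAS has no model and falls under the general statement "Descriptive statistics by treatment group were calculated to allow for comparisons between groups".

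**Where baseline pain might still appear.** The SAP also says "Descriptive statistics were calculated for patient and procedural characteristics across all treatment groups in phases 1 and 2". Pre-operative VAS is not named there. Even if it is meant to be included, a table of characteristics would show an imbalance without adjusting for it.

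**Rank of pain.** Section 4.0 states "The secondary outcome will be 6-hour postoperative opioid pain score". Section 1.0 instead names 6-hour opioid consumption as secondary and lists VAS pain as exploratory.

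**The concern.** A fall in opioid use is easier to read as a benefit if pain is no worse, so the pain comparison helps to interpret the primary result. Pain before surgery is a natural predictor of pain afterwards. It is planned for collection, and Section 10.0 describes no stratification on it. If it is left out of the analysis, the between-patient variation that it could explain stays in the standard error of the arm difference.

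The random subject effect does not do this work. It accounts for the correlation among one patient's repeated scores, but it leaves between-patient differences in the arm contrast. Only a patient-level covariate can remove part of them.

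**Working it through.** **Inputs from the documents**
- 20 patients per arm: "A sample size of 20 subjects per group (5 from phase 1 and 15 from phase 2"; phase 2 allocates 1:1 ("15 additional patients will be randomized to placebo and 15 to the optimal dose"). The alternative path in Section 6.0 (10 + 10) also gives 20 per arm.
- The only precision figure is ±0.64 SD. It is stated for opioid consumption; none is given for pain.

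**Assumptions**
- The correlation r between pre- and post-operative pain is not in the documents. I show 0 to 0.6.
- The pain comparison uses the same 20 per arm.

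**Step 1: reproduce the plan's figure.** Half-width = t(0.975, 38) × √(2/20) = 2.0244 × 0.3162 = 0.640 SD. This matches the stated figure, and in SD units it also applies to one unadjusted post-operative pain score.

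**Step 2: adjust for baseline.** Half-width = t(0.975, 37) × √(2/20) × √(1 − r²) × √(1 + 1/36). The t value, 2.0262, charges the lost degree of freedom; the last factor charges the estimation of the slope.

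| r | Adjusted half-width (SD) | Ratio to 0.640 |
|---|---|---|
| 0 | 0.650 | 1.015 |
| 0.1 | 0.646 | 1.010 |
| 0.2 | 0.636 | 0.994 |
| 0.3 | 0.620 | 0.968 |
| 0.4 | 0.595 | 0.930 |
| 0.5 | 0.563 | 0.879 |
| 0.6 | 0.520 | 0.812 |

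**Step 3: break-even.** Setting the two half-widths equal gives 1 − r² = (2.0244/2.0262)² × 36/37 = 0.971, so r is about 0.17.

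**Step 4: the repeated-measures setting.** Steps 1 to 3 treat a single score, whereas the SAP's model uses several. A simulation with 20 per arm and 8 assumed post-operative scores gave these standard errors for the arm difference:

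| ICC | r | Unadjusted SE (SD) | Adjusted SE (SD) |
|---|---|---|---|
| 0.5 | 0.3 | 0.238 | 0.220 |
| 0.5 | 0.5 | 0.239 | 0.180 |
| 0.7 | 0.6 | 0.272 | 0.197 |

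Both estimators were unbiased. The ICC, r and number of scores are all assumed.

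**Step 5: chance imbalance, for illustration.** The arms' mean baseline pain differs by more than 0.5 SD with probability 2 × [1 − Φ(0.5/√0.1)] = 0.114. At r = 0.5, a 0.5 SD imbalance shifts the unadjusted difference by 0.5 × 0.5 = 0.25 SD. That is 0.79 of the standard error, √(2/20) = 0.316 SD.

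**Step 6: missing baselines.** If patients without a pre-operative VAS are dropped, the Step 2 formula at r = 0.3 gives 0.637 SD with 19 per arm and 0.657 SD with 18. The first nearly cancels the gain; the second is worse than 0.640 SD unadjusted with all 20. At r = 0.5 with 18 per arm it gives 0.596 SD, so some gain survives.

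**The case against.** The strongest reply is that nothing here is an error. This is a pilot, and the SAP places pain among its additional outcomes. Describing such outcomes by arm is a defensible choice, and the unadjusted comparison is valid under randomisation. No sample size, dose decision or primary estimate would change. All of that stands.

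The size of the gain is also uncertain. It rests on r, and nothing in the documents supports 0.5 over 0.2. The baseline is a VAS taken before spine surgery; the modelled outcome is an NRS taken afterwards, in patients who are also receiving opioids. At r = 0.2 the gain is under 1%. This stands too, and is why the result is given as a range.

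It can further be said that quoting both a wider interval and a shift from imbalance counts one cost twice. That is correct: the sampling variance behind the unadjusted interval already includes chance imbalance in baseline pain. Step 5 illustrates that cost and does not add to it.

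The difference in scale is not a barrier. A covariate need not share the outcome's scale; only a change score would.

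What survives is the asymmetry. Adjustment loses about 1.5% at worst and gains about 12% to 19% at r of 0.5 to 0.6, from a measurement already planned.

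**Conclusion.** The omission is confirmed and worth correcting, but it is a modest loss of precision. For one post-operative score with 20 per arm, the half-width of 0.640 SD would become 0.636 to 0.520 SD for r from 0.2 to 0.6, with a small loss below about 0.17. This rests on the assumed r and on baselines being available for all 20 patients per arm.

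A reader might infer more, and the documents do not support it:
- **That the pain comparison is biased.** It is not; randomisation protects it on average.
- **That chronic pain is being ignored.** Section 5.0 requires elective spine surgery and says nothing about pain or its duration.
- **That a baseline score exists for every patient.** Section 10.0 plans the measurement; completeness is unknown.
- **That a secondary outcome is affected.** This follows from Section 4.0 only and conflicts with Section 1.0. Section 10.0 does not specifically schedule a 6-hour pain score, and the SAP sets out no analysis of one.
- **That the primary result is weakened.** The 12-hour opioid model and its ±0.64 SD are outside this point.

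**What to change.** In the SAP:
1. Add pre-operative VAS as a fixed covariate in the NRS pain mixed model.
2. Report PACU VAS as a baseline-adjusted between-arm difference with a 95% CI, alongside the descriptive statistics.
3. State a rule for a missing pre-operative VAS: impute the covariate simply, for example with the overall mean, so that no patient leaves the model.

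If the conflict between Sections 1.0 and 4.0 is resolved in favour of a 6-hour pain score, analyse that score in the same way.

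The change needs only SAP wording; the measurement is already planned. It costs one degree of freedom and, if the correlation is near zero, an interval up to about 1.5% wider.
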